3 STUDY ENDPOINTS

The intercurrent event of rescue medication use will be handled using Rescue Medication = Failure (RM=F), i.e., subjects who take rescue medication will be classified as failures for all efficacy assessments that are reported at or after taking rescue medication. The RM=F method will apply to all endpoints listed below, except the secondary endpoint of rescue medication use within 24 hours postdose.

3.1 Primary Endpoints

Pain freedom at 2 hours postdose will be assessed using the percentage of subjects with a pain intensity of none at 2 hours postdose. Pain intensity will be measured on a 4-point numeric rating scale (0=none, 1=mild, 2=moderate, 3=severe).

MBS freedom at 2 hours postdose will be assessed using the percentage of subjects with an MBS that is reported on study before dosing and is absent at 2 hours postdose. The MBS on study before dosing will be reported as nausea, phonophobia, or photophobia. Symptom status will be reported postdose as present or absent for each symptom (nausea, phonophobia, and photophobia).

3.2 Secondary Endpoints

1. Pain relief at 2 hours postdose will be assessed using the percentage of subjects with a pain intensity of none or mild at 2 hours postdose.
 2. Return to normal function at 2 hours postdose will be assessed using the percentage of subjects with a functional disability level of normal at 2 hours postdose in the subset of subjects with functional disability at the time of dosing. Functional disability level will be measured on a 4-point numeric rating scale (0=normal, 1=mildly impaired, 2=severely impaired, 3=requires bedrest), and functional disability will be defined as mildly impaired, severely impaired, or requires bedrest.
 3. Sustained pain relief at all time points from 2 to 24 hours postdose will be assessed using the percentage of subjects with pain intensities of none or mild at all time points from 2 to 24 hours postdose.
 4. Sustained pain relief at all time points from 2 to 48 hours postdose will be assessed using the percentage of subjects with pain intensities of none or mild at all time points from 2 to 48 hours postdose.
 5. Sustained pain freedom at all time points from 2 to 24 hours postdose will be assessed using the percentage of subjects with pain intensities of none at all time points from 2 to 24 hours postdose.
-

6. Sustained pain freedom at all time points from 2 to 48 hours postdose will be assessed using the percentage of subjects with pain intensities of none at all time points from 2 to 48 hours postdose.
 7. Phonophobia freedom at 2 hours postdose will be assessed using the percentage of subjects with phonophobia absent at 2 hours postdose in the subset of subjects with phonophobia present at the time of dosing.
 8. Photophobia freedom at 2 hours postdose will be assessed using the percentage of subjects with photophobia absent at 2 hours postdose in the subset of subjects with photophobia present at the time of dosing.
 9. Pain relief at 60 minutes postdose will be assessed using the percentage of subjects with a pain intensity of none or mild at 60 minutes postdose.
 10. Return to normal function at 60 minutes postdose will be assessed using the percentage of subjects with a functional disability level of normal at 60 minutes postdose in the subset of subjects with functional disability at the time of dosing.
 11. Pain relief at 30 minutes postdose will be assessed using the percentage of subjects with a pain intensity of none or mild at 30 minutes postdose.
 12. Return to normal function at 30 minutes postdose will be assessed using the percentage of subjects with a functional disability level of normal at 30 minutes postdose in the subset of subjects with functional disability at the time of dosing.
 13. Pain relief at 15 minutes postdose will be assessed using the percentage of subjects with a pain intensity of none or mild at 15 minutes postdose.
 14. Return to normal function at 15 minutes postdose will be assessed using the percentage of subjects with a functional disability level of normal at 15 minutes postdose in the subset of subjects with any level of functional disability at the time of dosing.
 15. Rescue medication use within 24 hours postdose will be assessed using the percentage of subjects who take rescue medication within 24 hours after taking study drug.
 16. Nausea freedom at 2 hours postdose will be assessed using the percentage of subjects with nausea absent at 2 hours postdose in the subset of subjects with nausea present at the time of dosing.
 17. Pain relapse from 2 to 48 hours postdose will be assessed using the percentage of subjects with a pain intensity of mild, moderate, or severe at any time point after 2 hours through 48 hours postdose in the subset of subjects with pain freedom at 2 hours postdose.
-

3.3 Exploratory Endpoint(s) (if applicable)

Not applicable.

3.4 Measures of Interest

Efficacy measures: Assessments of migraine pain intensity, migraine symptoms (phonophobia, photophobia, nausea), and functional disability

Safety measures:

- AEs
- ECGs
- Vital signs and physical measurements
- Clinical laboratory tests
- Sheehan Suicidality Tracking Scale (S-STTS)
- Nasal inspection

[figure not shown]
Outcomes research measures: Migraine Quality of Life Questionnaire (MQoL) and Preference of Medication (PoM)

4 STUDY PLAN

4.1 Study Design and Duration

This is a double-blind, randomized, multicenter, outpatient evaluation of the safety and efficacy of zavegepant as compared to matching placebo in the acute treatment of moderate or severe migraine. Subjects will be dispensed 1 Aptar UDS liquid spray device containing a single dose of zavegepant or a matching placebo. The total duration of the study will be approximately 11 weeks. This includes a 3-28 day Screening Period, a Treatment Phase that can last up to 45 days or until the subject has a migraine that reaches moderate or severe intensity, followed by an End of Treatment (EOT) Visit 7 (+2) days after the administration of study drug.

4.2 Study Schematic

4.3 Schedule of Assessments

Table 1: Schedule of Assessments

Procedure	Screening Visit ¹	Baseline/ Randomization Visit (Day 1) ²	Moderate or Severe Migraine Before Study Drug Administration ³	Post Study Drug Administration: 15, 30, 45, 60 and 90 minutes 2, 3, 4, 6, 8, 24 and 48 hours	End of Treatment Visit ^{4, 16}
Informed consent	X				
Duplicate subject check (in CTSdatabase)	X				
Inclusion/ Exclusion criteria	X	X			
Medical history	X				
Migraine History Assessment (signs/ symptoms/ prior treatment/ frequency/ intensity)	X				
Concomitant Medication paper diary ⁴	X	X	X	X	X
Rescue Medication paper diary ⁵		X	X	X	X
Randomize subject in IWRS ⁶		X			

Procedure	Screening Visit ¹	Baseline/ Randomization Visit (Day 1) ²	Moderate or Severe Migraine Before Study Drug Administration ³	Post Study Drug Administration: 15, 30, 45, 60 and 90 minutes 2, 3, 4, 6, 8, 24 and 48 hours	End of Treatment Visit ^{14, 16}
Physical Examination	X				X
Nasal Inspection ⁷	X	X			X
Vital Signs/ Physical Measurements ⁸	X	X			X
Adverse Event and Serious Adverse Event Assessment ⁹	X	X	X	X	X
Sheehan Suicidality Tracking Scale (S-STSS) ¹⁰	X	X			X
ECG	X				X
Clinical Safety Laboratory Testing	X				X
Liver Function Tests (LFTs)	X				X
Lipid Panel	X				X
FSH, if applicable, to determine WOCBP status	X				
Pregnancy Test ¹¹	X (Serum)	X (Urine)	X (Urine)		X (Serum)
Urinalysis	X				X
Urine drug screen for drugs of abuse	X				X

Procedure	Screening Visit ¹	Baseline/ Randomization Visit (Day 1) ²	Moderate or Severe Migraine Before Study Drug Administration ³	Post Study Drug Administration: 15, 30, 45, 60 and 90 minutes 2, 3, 4, 6, 8, 24 and 48 hours	End of Treatment Visit ^{4, 16}
Clinical Drug Supplies/ Study Supplies					
eCOA handheld device assigned to subject		X			
Patient education: study medication administration with instruction for use document		X			
Patient education: eCOA handheld device subject online training/ training device		X			
Dispense study medication ¹²		X ²			
Administer study medication			X ¹²		
Enter use of study medication in eCOA handheld device			X ¹²		
eCOA handheld device returned/ reviewed for completeness ¹³					X
Return unused or used study medication to site for reconciliation					X

Procedure	Screening Visit ¹	Baseline/ Randomization Visit (Day 1) ²	Moderate or Severe Migraine Before Study Drug Administration ³	Post Study Drug Administration: 15, 30, 45, 60 and 90 minutes 2, 3, 4, 6, 8, 24 and 48 hours	End of Treatment Visit ^{4, 16}
Efficacy and Outcomes Research Assessments¹²					
Assessments of migraine pain, migraine symptoms (phonophobia, photophobia, and nausea) and functional disability ¹⁴			X	X	
MQoL (Migraine Quality of Life Questionnaire) ¹⁴				X (24-hour assessment)	
Preference of Medication (PoM) ¹⁴				X (24-hour assessment)	

¹ **Screening Phase** will be 3 - 28 days. Subject should be entered in the IWRS after they sign the informed consent form to obtain their study subject identification code.

² The **Baseline/ Randomization Visit** may only occur *after* all screening procedures are completed and the subject meets all inclusion/exclusion criteria. If the subject does not meet all eligibility requirements, the subject should be screen failed in the IWRS. Subjects may be re-screened with a new subject ID.

³ Subjects will use their assigned eCOA handheld device before study drug administration to answer questions about their migraine symptoms upon experiencing a moderate or severe migraine headache. The subject will administer zavegepant or matching placebo if the following criteria are met: 1) the headache remains moderate or severe; 2) the subject has completed all required migraine assessment questions in the handheld, including their current most bothersome migraine symptom, and 3) the subject has not already taken prohibited medications.

⁴ Subjects should keep track of their concomitant medications on the IRB approved study paper diary provided throughout the study. A concomitant medication paper diary will be provided to subjects at the Screening visit. These paper diaries should be returned to the investigational site at each visit for review and electronic data capture (EDC) entry. The paper diaries should be kept as source documents.

⁵ Subjects should keep track of their rescue medications on the IRB approved study paper diary provided throughout the study. A rescue medication paper diary will be provided to subjects at the Baseline visit. Reference the rescue medication section 5.5 for additional information. These paper diaries should be returned to the investigational site for review and electronic data capture (EDC) entry. The paper diaries should be kept as source documents.

⁶ The randomization visit is considered day 1 out of the 45 days subjects have to treat and report a migraine in their handheld device. Subjects will be randomized in the IWRS and will be stratified by answering “yes” or “no” to prophylactic migraine medication use in the IWRS.

⁷Nasal inspection – The nasal passages and turbinates will be visually inspected with a nasal speculum or otoscope at the Screening, Baseline and end of EOT Visits to detect evidence of nasal inflammation or edema.

⁸Height will only be captured at the Screening Visit. Weight, body temperature, respiratory rate, blood pressure and heart rate will be collected at all time points where indicated. Sitting arterial systolic and diastolic blood pressure and pulse rate will be measured.

⁹SAEs are reported from the time of signed informed consent and non-serious AEs are reported from the Baseline Visit. All ongoing non-serious AEs and SAEs will be followed to resolution or until the Investigator deems there will be no further status change. SAEs that occur during the treatment period should be reported to site in real time. Non-serious AEs that occur during the treatment period should be reported to the site at the EOT Visit.

¹⁰The S-STs will be clinician administered on site with a paper form. The source document will be provided digitally by Biohaven. The assessment period for completing the scale will be 30 days prior to the Screening Visit, and since the last visit for the Baseline/Randomization and EOT Visits.

¹¹For WOCBP: A serum pregnancy test will be collected at the Screening and EOT Visits as part of the standard laboratory tests. Confirmatory urine pregnancy test for WOCBP will be completed on site at the Baseline Visit and any subsequent visits for confirmation at the Investigator's discretion. Home pregnancy test will be provided to WOCBP after completion of Baseline Visit. WOCBP subjects must complete the urine pregnancy test at home **prior** to taking study drug.

¹²Subjects should be instructed that the dose should be administered once the migraine attack reaches moderate or severe pain and after the subject has completed all required migraine assessments in the handheld. The handheld will prompt the subject when they should administer study drug.

¹³Site staff to review and confirm all data points are transferred from the handheld and reset handheld for future subject use, **PRIOR** to the subject leaving the clinic.

¹⁴The Functional Disability, MQoL and Preference of Medication scales will be captured in the handheld device. Subjects will also be asked about their most bothersome symptom at the time of reporting and treating a qualifying migraine before study drug administration.

¹⁵Subjects will return to the site for their EOT Visit (after assessments in the handheld are completed) within 7 (+2) days after dosing with study drug. The “+2” day window is included for scheduling purposes only.

¹⁶Every effort should be made to conduct the EOT Visit within the specified window of 7 (+2) days after dosing with study drug. However, if necessary due to local COVID-19 safety requirements, the EOT Visit may be performed outside of the window by an additional 5 days in order to minimize any potential risks to subject safety and to comply with governmental and institutional guidance. See Section 4.3.5 for more information.

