- a) History of drug or other allergy which, in the opinion of the Investigator, makes the subject unsuitable for participation in the study.
- 4) Sex and Reproductive Status
- a) Females of child-bearing potential who are unwilling or unable to use an acceptable contraceptive method or abstinence to avoid pregnancy for the entire study period and for 90 days after the study.
-

- b) Women who are pregnant, lactating or breastfeeding.
 - c) Women with a positive pregnancy test.
- 5) ECG and Laboratory Test Findings
- a) Estimated glomerular filtration rate (eGFR) according to the re-expressed abbreviated (4-variable) Modification of Diet in Renal Disease (MDRD) Study equation ≤ 40 ml/min/1.73m².
 - b) Corrected QT interval > 470 msec (QTc by method of Frederica), at Screening.
 - c) Left Bundle Branch block.
 - d) Right Bundle Branch Block with a QRS duration ≥ 150 msec.
 - e) Intraventricular Conduction Defect with a QRS duration ≥ 150 msec.
 - f) Serum bilirubin (Total, Direct or Indirect) > 1.5 x ULN are excluded. However, abnormal values of between 1-1.5x ULN may be considered but must be repeated once for confirmation during the screening period. Repeat results **must** be the same or lower than the first lab result in order to remain eligible for the study. Subjects must be excluded if repeat is > 1.5 x ULN.
 - g) Neutrophil count $\leq 1000/\mu\text{L}$ (or equivalent).
 - h) AST (SGOT) or ALT (SGPT) >1.5 x ULN are excluded. However, abnormal values of between 1-1.5x ULN may be considered but must be repeated once for confirmation during the screening period. Repeat results **must** be the same or lower than the first lab result in order to remain eligible for the study. Subjects must be excluded if repeat is >1.5 x ULN.
- 6) Other Exclusion Criteria:
- a) Prisoners or subjects who are involuntarily incarcerated.
 - b) Subjects who are compulsorily detained for treatment of either a psychiatric or physical (e.g., infectious disease) illness.
 - c) Score of > 0 on the Sheehan Suicidality Tracking Scale for the period of 30 days prior to Screening and during the study.
 - d) Participation in clinical trial with non-biological investigational agents or investigational interventional treatments (last study visit occurring) within the 30 days prior to Baseline Visit.
-

- e) Subjects who have previously participated in any BHV-3500 study (re-screens for this study, (BHV3500-301), may be considered, as described in inclusion criteria 6b above).

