The S-STs is a prospective clinician administered rating scale that contains questions that track both treatment-emergent suicidal ideation and behaviors^{13,14}. The S-STs will be completed on a paper form at the site. At the screening visit, the recall period for completing the S-STs is within the last 30 days prior to the screening visit; at all other visits, the recall period for completing the S-STs is since the last visit (reference [Table 1](#)). Subjects who have a S-STs score of >0 should be evaluated by the Investigator. If the Investigator determines that a subject is at risk of suicide or self-harm, appropriate measures to ensure the subject's safety and obtain mental health evaluation must be implemented. In such circumstances, the subject must immediately be discontinued from the study. The event should be recorded as either an AE or SAE as determined by the investigator and reported within 24 hours to the Sponsor.

6.4 **Efficacy Assessments**

6.4.1 ***Pain***

Subjects record their headache pain intensity using a 4-point numeric rating scale (none, mild, moderate, severe) in the eCOA handheld device at the time points indicated in [Table 1](#).

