Safety Endpoint	Frequency of adverse events (AEs) of at moderate or severe intensity, serious adverse events (SAEs), clinically relevant laboratory test abnormalities, and nasal inspection abnormalities
Summary	Number and percentage of subjects with safety events and findings for the safety analysis set
Intercurrent Events	Rescue medication use: Treatment policy strategy, i.e., no accounting for intercurrent event
Objective	S-STS
Safety Endpoint	Change from baseline in the total score at end of treatment visit
Summary	Percentage of subjects in each change from baseline category (< -1, -1, no change, 1, > 1) by treatment group for the safety analysis set with S-STS data
Intercurrent Events	Rescue medication use: Treatment policy strategy, i.e., no accounting for intercurrent event

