6.4.4 Electrocardiogram

ECG parameters include RR, QRS, PR, QT, QTcF, and ventricular heart rate, which are measured with both date and time by the external source CCI

A by-subject listing of ECG results is provided for the enrolled analysis set, and displays COVID-19 visit impact code for visits impacted by COVID-19 (see Section 9.1.5.2).

6.4.4.1 *ECG Changes from Baseline*

Values and changes from baseline in ECG parameters are tabulated as continuous variables at baseline and the end of treatment visit.

If there are multiple values on the same measurement date and time, then the value with the last ECG reference identifier is used.

6.4.4.2 *ECG Interpretation Shifts from Baseline to Worst Category*

ECG interpretation shifts from baseline to the worst on-treatment category are tabulated as the number and percentage of subjects with normal, abnormal, and clinically significant abnormal interpretations.

6.4.4.3 *ECG Abnormalities*

On-treatment ECG abnormalities are tabulated as the number and percentage of subjects in the categories specified in the Zavegepant Core SAP.

6.4.5 **S-STS**

The S-STS is a prospective rating scale that contains 16 patient-reported questions and 6 clinician-reported questions to track both treatment-emergent suicidal ideation and behaviors. Refer to the Zavegepant Core SAP for calculation of the S-STS ideation subscale, behavior subscale, and total scores.

Values and changes from baseline in the self-reported S-STS ideation subscale, behavior subscale, and total score are tabulated as continuous variables at baseline and the end of treatment visit. The number and percentage of subjects in each change from baseline category (i.e., < -1, -1, no change, 1, > 1) are also presented for the ideation subscale, behavior subscale, and total score.

A by-subject listing of S-STS is provided for the enrolled analysis set, and displays COVID-19 visit impact code for visits impacted by COVID-19 (see Section 9.1.5.2).

Refer to the Zavegepant Core SAP for the listing contents.

6.4.6 **Safety Narratives**

A by-subject listing of safety narrative subject identifiers is provided for the following select events and analysis sets as columns:

- All deaths for the enrolled analysis set
- On-treatment SAEs for the safety analysis set treated with zavegepant
- All AEs leading to discontinuation of study drug for the safety analysis set treated with zavegepant

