7.2 Analysis Periods

Analysis periods are defined as follows:

- Pre-treatment: measurement date/time at or before the study drug start date/time. This period is used to derive baseline values and to assess pre-treatment endpoints. Note that all measurements are pre-treatment for subjects in the enrolled analysis set with missing study drug start date.
- On-treatment: measurement date/time after the study drug start date/time. This period is used to assess safety endpoints on treatment. Note that AEs with imputed start date equal to the study drug start date are part of this period.

See Section 7.1 for derived date/times for determining analysis periods.

If measurement time is missing, not collected, or not applicable for a parameter, then the measurement date is compared to the derived date.

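### The end-of-treatment S-STS is not anchored to dosing, so a positive score cannot be placed before or after the single dose, yet the SAP counts it as on-treatment

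*Protocol*

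**What the plan says.** **Recall period.** Protocol 4.3, Table 1, schedules the S-STS at Screening, Baseline/Randomization and EOT only. Screening looks back 30 days. For the other two visits footnote 10 gives the period as "since the last visit for the Baseline/Randomization and EOT Visits", and Protocol 6.3.5 agrees: "at all other visits, the recall period for completing the S-STs is since the last visit". The same section says that the scale's questions "track both treatment-emergent suicidal ideation and behaviors".

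**Time of dosing.** Table 1, footnote 6: "The randomization visit is considered day 1 out of the 45 days subjects have to treat and report a migraine in their handheld device". EOT follows within 7 (+2) days of the dose, with a possible 5 further days for COVID-19 reasons (footnotes 15 and 16).

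**Analysis.** The S-STS endpoint in SAP 3.2.3, Table 3, is "Change from baseline in the total score at end of treatment visit", shown as the percentage of safety-set subjects in each change category by treatment group. SAP 6.4.5 adds: "Values and changes from baseline in the self-reported S-STS ideation subscale, behavior subscale, and total score are tabulated", as continuous variables and in change categories. SAP 7.2 defines on-treatment as "measurement date/time after the study drug start date/time. This period is used to assess safety endpoints on treatment". SAP 6.4 has the safety listings identify on-treatment data.

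**Eligibility.** Exclusion 6(c) in Protocol 5.3 reads "Score of > 0 on the Sheehan Suicidality Tracking Scale for the period of 30 days prior to Screening and during the study", so baseline is essentially 0 in eligible subjects.

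**The concern.** Assigning a result to a period by its measurement date suits point measurements such as laboratory tests or ECGs. The S-STS instead reports on an interval, and here the interval straddles the dose. Take a subject with ideation on day 10 who doses on day 40. The EOT form is dated after the dose, baseline is 0, and the subject appears as an on-treatment increase although nothing had been taken when the ideation occurred. Neither the protocol nor this SAP asks for an onset date, a dose-anchored recall or a split score.

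Positive scores are likely to be few, so their interpretation will rest on individual cases. Timing relative to the dose is the first thing a reader of such a case needs. SAP 9.2 does not help: it counts a score above 0 as a deviation through randomization, and at any time in the study only for subjects who were not dosed. In dosed subjects, ideation between randomization and dosing is neither flagged nor separable.

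**Working it through.** **1. The plan's timeline.** Screening up to 28 days, treatment phase up to 45 days, EOT 7 days after dosing: 28 + 45 + 7 = 80 days = 11.4 weeks. This reproduces the approximately 11 weeks in Protocol 4.1.

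**2. Longest predose interval.** Randomization is day 1 and the last dosing day is day 45: 45 − 1 = 44 days. Predose share of the EOT recall = predose days / (predose days + days from dose to EOT):

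| Dose to EOT | Total recall | Predose share |
|---|---|---|
| 7 days | 51 days | 44/51 = 86% |
| 9 days (+2 window) | 53 days | 44/53 = 83% |
| 14 days (COVID-19 extension) | 58 days | 44/58 = 76% |

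These are maxima. The Baseline score, by comparison, covers 3 to 28 days.

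**3. A more typical share (assumption).** The documents give no time-to-dose distribution. Assume an exponential wait at rate λ per day, truncated at T = 44 days, with mean = 1/λ − T·exp(−λT)/(1 − exp(−λT)). The rates of 2 and 8 per month are the entry limits in Protocol 5.2; 4 is intermediate. The last row sets λ so that 10% remain undosed, matching the 90% expected to have a headache in the allotted time (Protocol 9.1). Pooled share of recalled person-days = mean/(mean + 7).

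| Attack rate | Mean predose days | Predose share |
|---|---|---|
| 2 per month (λ = 2/30) | 12.5 | 64% |
| 4 per month (λ = 4/30) | 7.4 | 51% |
| 8 per month (λ = 8/30) | 3.7 | 35% |
| 10% undosed (λ = −ln 0.1/44) | 14.2 | 67% |

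Truncating at 45 days instead moves the last row to 14.5 days and 14.5/21.5, about 68%. The range is therefore about 35% to 68%.

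**4. Effect on the comparison with placebo (assumption).** Let the background hazard of a positive response be h = 0.0005 per day, doubled on zavegepant for 7 days after dosing, with 630 subjects per arm (the planned evaluable number, standing in for the safety set). With d predose days, placebo risk = 1 − exp(−h(d + 7)) and zavegepant risk = 1 − exp(−h(d + 2×7)).

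| Predose days d | Placebo | Zavegepant | Difference (points) | Ratio | Power |
|---|---|---|---|---|---|
| 0 | 0.35% | 0.70% | 0.35 | 2.00 | 13.5% |
| 16 | 1.14% | 1.49% | 0.35 | 1.30 | 7.7% |
| 44 | 2.52% | 2.86% | 0.34 | 1.14 | 5.6% |

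The difference hardly moves; the ratio and the power fall. The pattern is the same for hazards from 0.0002 to 0.001 per day and postdose hazard ratios of 2 and 3. With no drug effect the difference is 0 for every d.

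**The case against.** The strongest reply is that exploratory objective 11 compares zavegepant with placebo. Recall rules are identical in both arms, allocation is 1:1 and double-blind, and predose ideation cannot depend on a drug not yet taken. It is therefore balanced in expectation and creates no false signal on average. This stands. A reader might infer from the mixed window that the S-STS cannot answer objective 11; the documents do not support that.

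Nor is a diluted ratio the right headline. The SAP plans percentages by change category and descriptive statistics, with no ratio and no specified test. On the difference scale almost nothing is lost, and under the assumed rates even perfect anchoring gives only 13.5% power. This also stands.

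Unequal recall lengths at Baseline and EOT matter only for a within-arm reading, because baseline is essentially 0 and the change is close to the EOT score itself.

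A further reply is that dated evidence already exists. On-treatment suicidality AEs are tabulated (SAP 6.4.1.4) and trigger narratives for zavegepant-treated subjects (SAP 6.4.6), and AEs are placed by start date. This stands only in part. Protocol 6.3.5 asks for evaluation of any score above 0 but ties AE or SAE recording to a judgement that the subject is at risk, so a positive score without that judgement need not become a dated AE. Protocol 8 also discourages asking about specific AEs, which leaves the S-STS as the scheduled direct inquiry.

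Finally, the S-STS form and the Zavegepant Core SAP are not available here and may date responses. That limits certainty about what is collected. And the SAP 6.4.5 table is labelled by visit, not as on-treatment; the period label comes from SAP 7.2 and the listings.

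**Conclusion.** The point holds as one of classification and precision. The EOT S-STS recalls everything since Baseline/Randomization, up to 44 predose days, and is then treated as on-treatment by its date. An individual positive score cannot show whether ideation came before or after the dose, so it does not by itself establish treatment emergence. In the between-arm comparison the predose portion is noise, not bias, and objective 11 can still be addressed.

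The 44-day maximum and the 86%, 83% and 76% shares follow from the documents' visit windows. The 35% to 68% range rests on assumed exponential waits with EOT at 7 days, and the risk and power figures on assumed ideation hazards. The 86% should not be read as the usual case. This is a cheap improvement to an exploratory safety measure and has no bearing on the co-primary analysis.

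**What to change.** **Protocol Table 1, footnote 10, and 6.3.5.** Keep the full recall since the last visit, so that no safety coverage is lost. For dosed subjects with any positive EOT response, have the clinician record whether it occurred before or after study drug was taken, or score the two intervals separately. The dose time is already captured in the eDiary. Undosed subjects need no change.

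**SAP 3.2.3, Table 3, and 6.4.5.** Add the number and percentage of safety-set subjects with a postdose S-STS score above 0, by treatment group. State that positives confined to the predose interval are not labelled on-treatment, as an exception to the date rule in SAP 7.2.

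**Cost.** One added item on the paper form and a few lines of SAP text, with no new visit or instrument. The attribution is retrospective and carries some recall error, but takes only a minute or two for the few subjects with a positive response.
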